#### Abstract

**Introduction:** Helicobacter pylori (H. pylori) infection remains a major public health problem, with an estimated prevalence of over 50% worldwide and 60-86% for Portugal. H. pylori is associated with significant morbidity and mortality from peptic ulcerative disease to gastric cancer, whose eradication therapy has proven to be effective in preventing these complications. Factors involved in the development of these conditions include H. pylori virulence, host genetic factors and gut microbiota. Given the increasing pattern of antibiotic resistance evidenced by this bacterium and the scarcity of available antibiotic therapy, both in Portugal and worldwide, there is not enough evidence on the best eradication strategy. Regarding the uncertainties about the potential negative impact of indiscriminate use of eradication therapy on gut microbiota, either by proton pump inhibitors or by antibiotics per se, there is an overriding need for evidence about the real impact of this therapy on gut flora and possible clinical consequences in immunological, metabolic, nutritional and oncological terms. **Objectives:** Comparative evaluation of the efficacy of the different quadruple therapy regimens recommended for the H. pylori eradication. Comparative evaluation of the safety profile in terms of clinical, immunological and gut microbiota impact of the different therapies for the H. pylori eradication. **Methods:** Prospective longitudinal multicentre study of total of patients with gastric infection by H. pylori, diagnosed by C-urea breath test or histological analysis of gastric biopsies and clinical indication for its eradication, referred to the different participating Portuguese hospital units and a blind randomized controlled clinical trial of the efficacy and safety of the different quadruple therapy regimes recommended for the H. pylori eradication. This study will be carried out in 4 phases: Phase 1 - Recruitment and randomization of patients by the different quadruple eradication schemes with and without bismuth (5 parallel arms); Phase 2 - H. pylori eradication with evaluation of the efficacy and safety rates at 1 month and the absence of reinfection at 12 months after treatment and collection of stool samples before and after the eradication therapy for evaluation of changes in gut microbiota; Phase 3 - Analysis of richness, diversity and uniformity of gut microbiota by DNA sequencing using the hypervariable region of the ribosomal 16S bacteria gene as a taxonomic identification marker and their clinical impact on immunology, metabolism and nutrition at 12 months after the H. pylori eradication therapy; and Phase 4 - Analysis of immunological changes through the study of cell populations by flow cytometry (CD4+, CD8+, B-cell, T-cell, natural killer cells, cells ratio) and cytokines, chemokines and growth factors by xMAP/Luminex before and 12 months after the H. pylori eradication therapy. **Expected results, impact and scientific outputs:** Given the high rate of triple therapy inefficacy, high antibiotic resistance and the scarcity and controversy of existing literature on quadruple regimens, there may be relevant differences in the approved quadruple regimens for the H. pylori eradication, being necessary to define which is the most effective and safe in Portugal, decreasing the rate of ineffectiveness and exposure to multiple antibiotics. The homeostasis of gut microbiota is significantly changed after H. pylori eradication and this modification may be

substantially different according to the therapeutic scheme used, with clinical implications on immunology, metabolism and nutrition. Thus, a randomized trial to compare quadruple regimens is needed, allowing in the future, an individualized selection of the *H. pylori* eradication regimen, taking into account the higher efficacy and safety and lower gut dysbiosis and its systemic consequences, in short and long term. Modulating gut microbiota therapies, including prebiotics, probiotics, symbiotics, fecal microbiota transplantation and perhaps targeted-immunotherapy may be beneficial as adjuvant therapy to existing *H. pylori* eradication regimens, in a systematic way or for some therapeutic regimes or risk groups.

## Literature Review

*Helicobacter pylori* (*H. pylori*) infection remains a major public health problem, affecting over 50% of the worldwide population and 60-86.4% of the Portuguese population. This bacterium is responsible for chronic active gastritis, likely to develop into peptic ulcerative disease, atrophic gastritis, gastric adenocarcinoma and mucosal-associated lymphoid tissue lymphoma. Factors involved in the development of these conditions include bacterial virulence, host genetic factors and gut microbiota. *H. pylori* eradication therapy has been shown to be effective in preventing the development or recurrence of these complications. However, the increase in primary and secondary resistance of this bacterium to most antibiotics has reduced the efficacy of this therapeutic strategy. As in the rest of Europe, overall resistance to multiple antibiotics is high in Portugal, with a prevalence of 42-50% for clarithromycin, 25-34.4% for metronidazole, 18-33.9% for levofloxacin, 0.2-0.6% for tetracycline, 0.1-0.6% for amoxicillin and 20% for clarithromycin and metronidazole. Taking into account the pattern of *H. pylori* antibiotic resistance in Portugal and the selection flowchart proposed by [GrLeWu14], the currently recommended therapeutic regimens include quadruple therapies: sequential, hybrid, concomitant with bismuth and concomitant bismuth-free. However, some studies including quadruple schemes have shown unsatisfactory results, not exceeding 90% considered as the minimum efficacy rate. Given the high rate of resistance of *H. pylori* to nitroimidazoles registered in Portugal, it would be worth considering therapeutic optimization with metronidazole 500mg tid and not only bid. Thus, at present, there are no solid data that allow us to state the best therapeutic option in this country, being essential to conduct a randomized study to definitively resolve this uncertainty. Animal and human studies have shown that *H. pylori* results in changes in gut microbiota. Human gut microbiota represents a dynamic and complex ecosystem in close linking with the immune system, regulating gastrointestinal homeostasis. It is composed mostly of Gram-negative anaerobic bacilli, mainly Bacteroidetes and Fusobacteria. Gut dysbiosis has been associated with immune, metabolic, nutritional and oncological changes, such as the development of several gastrointestinal and systemic conditions such as inflammatory bowel disease, obesity, diabetes mellitus, metabolic syndrome, dyslipidemia, asthma and allergies. However, the interactions between *H. pylori*, gut microbiota and host pathophysiology are still far from being understood. Similarly, there are also uncertainties regarding the potential negative impact of indiscriminate use of *H. pylori* eradication therapy on the gut microbiota, mediated by either proton pump inhibitors or antibiotherapy. In some recent studies, eradication of *H. pylori* has been associated with a decrease in butyrate-producing bacteria (such as *Faecalibacterium prausnitzii*), Proteobacteria, Actinobacteria and Firmicutes, and an increase in several potentially harmful bacteria such as Bacteroidetes and the Bacteroidetes:Firmicutes ratio. These changes persist until 12-18 months after *H. pylori* eradication therapy, although in one study changes in gut microbiota

were documented up to 4 years after eradication. Given that only approximately 20% of *H. pylori* infected individuals will develop complications and the potentially harmful effects of antibiotherapy use on the gut microbiota, further studies are needed to understand the complex interactions between the *H. pylori*-gut microbiota-host axis in order to identify individuals at increased risk of long-term sequelae. *H. pylori* gastric infection can induce humoral and cellular immune responses. Some studies showed an increase of Th1 and Th17 cells into the gastric mucosa and activation of humoral immunity, Th2 polarization and some cytokines such as IL1 $\beta$ , IL4 and IL5 in the peripheral blood, during *H. pylori* infection. Data on immunological changes after eradication of *H. pylori* are very scarce, with one study showing a downregulation of the Th1 cytokines, a prolonged Th2 response with persistent raised IL4 levels and markedly reduction of the T-regulatory response. To date, there is a lack of evidence on the impact of *H. pylori* eradication therapy, as well as the comparative impact of different therapeutic regimens used in gut microbiota, immunological changes and their implication in clinical practice.

## **Plan and Methods**

### **A. Research hypothesis**

The authors hypothesize that there are relevant differences in the quadruple schemes that can be used in the *H. pylori* eradication therapy, being necessary to define which of them is the most effective in Portugal, in order to decrease the failure rate and subsequent exposure to potentially harmful effects of antibiotics. Additionally, the authors assume that homeostasis of gut microbiota is significantly changed after *H. pylori* eradication therapy and these alterations may not be similar among the different recommended therapeutic regimens. Likewise, these alterations may have clinical implications in the immunological, metabolic and nutritional status of individuals submitted to this therapy. Hypothesis: There is a quadruple *H. pylori* eradication therapy associated with a higher efficacy and safety than other currently approved quadruple regimens in terms of clinical, immunological and microbiota changes in *H. pylori* gastric infection.

### **B. Objectives**

- To determine and compare the efficacy of the different therapeutic regimens recommended as *H. pylori* eradication therapy;
- Comparative evaluation of the safety profile in terms of clinical, immunological and gut microbiota impact of the different recommended therapies for the *H. pylori* eradication:
- To evaluate the changes in gut microbiota after the *H. pylori* eradication therapy;
- Compare the changes in gut microbiota induced by the different therapeutic regimens for *H. pylori* eradication and evaluate their clinical implications on immunology, nutrition and metabolism;
- To evaluate the immunological changes after the *H. pylori* eradication therapy;
- Compare the immunological changes induced by the different therapeutic regimens for *H. pylori* eradication and evaluate their clinical implications.

### **C. Expected results, study clinical impact and scientific outputs**

Given the high rate of triple therapy inefficacy, high antibiotic resistance and the scarcity and controversy of existing literature on quadruple regimens, there may be relevant differences in the approved quadruple regimens for the *H. pylori* eradication, being necessary to define which is the most effective and safe in Portugal, decreasing the rate of ineffectiveness and exposure to multiple antibiotics. The homeostasis of gut microbiota is significantly changed after *H. pylori* eradication and this modification may be substantially different according to the therapeutic scheme used, with clinical implications on immunology, metabolism and nutrition. Thus, a randomized trial to compare quadruple regimens is needed, allowing in the future, an individualized selection of the *H. pylori* eradication regimen, taking into account the higher efficacy and safety and lower gut dysbiosis and its systemic consequences, in short and long term. Modulating gut microbiota therapies, including prebiotics, probiotics, symbiotics, fecal microbiota transplantation and perhaps targeted-immunotherapy may be beneficial as adjuvant therapy to existing *H. pylori* eradication regimens, in a systematic way or for some therapeutic regimens or risk groups.

## **D. Methodology and Phases of project development**

### **D.1 Type of study**

Prospective longitudinal multicentre study and a blind randomized controlled trial involving several hospital units in Portugal. Regarding the evaluation of gut microbiota and immunological changes, the study will be blinded, since the researchers responsible for sequencing and immunological analysis will not know the therapeutic scheme applied. The trial will be registered on the <https://clinicaltrials.gov> platform.

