surgery or neoplasia; Previous H. pylori eradication therapies; Antibiotic or probiotic therapies in the month prior to recruitment; Use of proton pump inhibitors, other antacids or gastric mucosal protection agents in the 2 weeks prior to recruitment; Corticosteroids or immunomodulatory therapy in the month prior to recruitment; Immunodeficiency; Insulin-treated diabetes mellitus; Obesity (Body mass index  $\geq 30\text{Kg/m}^2$ ); Use of laxative therapy in the 15 days prior to recruitment; Decompensated heart, liver, kidney or respiratory diseases and; Refusal or inability to give informed consent. H. pylori eradication schemes: Each patient will randomly follow one of the five H. pylori eradication schemes (5 parallel arms): sequential, hybrid, concomitant with bismuth and two concomitants bismuth-free. Sample size calculation: Assuming the estimated prevalence of H. pylori gastric infection in Portugal in adults is 86.4%, it was determined that for a 95% confidence level and a 10% sampling error it will be necessary to include 46 patients in each of the 5 arms of the study, making a total of 230 patients.

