#### **Phase 2.** Eradication of H. pylori and collection of stool and blood samples

Stool samples shall be collected from patients and analyzed on 3 occasions: before (baseline), after stopping treatment (Day 10 or 14) and 1 month after treatment (Day 40 or 44). Blood samples will be collected and analyzed on 2 occasions: before (baseline) and 12 months after treatment. Efficacy and safety rates of H. pylori eradication will be determined for each therapeutic regimen. Carbon 13-labeled urea breath test or upper gastrointestinal endoscopy with biopsies will be performed at 1 month (D40 or D44) and 12 months after treatment. The clinical data, adherence and therapy-related adverse events will be recorded at baseline and during follow-up at 1 and 12 months post-eradication.

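### The trial is labelled blind for efficacy and safety, but masking is described only for the sequencing and immunology researchers, so the label is unsupported for eradication, adherence and clinical adverse events

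*Combined protocol and SAP*

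**What the plan says.** The abstract (Methods) describes "a blind randomized controlled clinical trial of the efficacy and safety of the different quadruple therapy regimes recommended" for eradication. The first sentence of D.1 repeats the label without qualification: "Prospective longitudinal multicentre study and a blind randomized controlled trial involving several hospital units in Portugal".

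The next sentence of D.1 is the only account of masking in the document. It begins "Regarding the evaluation of gut microbiota and immunological changes, the study will be blinded" and gives as the reason that "the researchers responsible for sequencing and immunological analysis will not know the therapeutic scheme applied".

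D.3, Phase 1, lists the arms as "sequential, hybrid, concomitant with bismuth and two concomitants bismuth-free". D.3, Phase 2, times the second stool sample "after stopping treatment (Day 10 or 14", so there are two possible end-of-treatment days. Eradication is checked at 1 and 12 months by breath test or by endoscopy with biopsies. At the same visits, "adherence and therapy-related adverse events will be recorded".

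**The concern.** Comparing the efficacy of the regimens is the first objective in section B, and the safety profile, including its clinical part, is the second. A reader of the abstract would take both comparisons to be masked. The masking described reaches neither eradication nor clinical adverse events.

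Two things are at stake. A report that repeats the abstract would claim a property that the described design does not have. And where an outcome depends on judgement (whether an event is attributed to treatment, whether a biopsy shows the organism, whether a patient was adherent), knowledge of the regimen can shift the result differently in different arms. That part is largely avoidable at low cost. Events that are never recorded cannot be reliably recovered at analysis.

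**Working it through.** **1. Masking by role and outcome, as described**

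| Outcome | How it is determined | Masking described |
|---|---|---|
| Gut microbiota | Sequencing (Phase 3) | Yes, D.1 |
| Immunology | Flow cytometry and Luminex (Phase 4) | Yes, D.1 |
| Eradication by breath test | Rise of more than 4 per thousand over baseline at 30 minutes (stated in Phase 1 for inclusion) | None |
| Eradication by histology | Organism detected in at least one biopsy (stated in Phase 1 for inclusion) | None |
| Adherence | Recorded at visits (Phase 2) | None |
| Clinical adverse events | Therapy-related events recorded at visits (Phase 2) | None |

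The document does not mention masking of patients, treating staff, breath-test operators, pathologists, or those who record adherence and adverse events.

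**2. Could the design conceal the regimen anyway?** The arms differ in composition (with and without bismuth) and in how the drugs are combined over time (sequential, hybrid, concomitant). The two end-of-treatment days are most naturally read as depending on the regimen. No placebo, double-dummy or matched packaging is described. Concealment therefore cannot be presumed.

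**3. Where judgement enters.** The breath test is read against a number, which leaves little room for the reader. Histology depends on a reader, but Phase 2 gives no rule for choosing between the two methods, so the share of patients assessed by histology is unknown. For adverse events, a filter on attribution means that someone's judgement decides whether an event exists in the data at all.

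**4. Sizes**

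*The plan's own figure.* D.3 gives 46 per arm from a proportion of 0.864, 95% confidence and 10% sampling error. n = 1.96² × 0.864 × 0.136 / 0.10² = 45.14, rounded up to 46, and 46 × 5 = 230. This reproduces. It does not depend on masking.

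*Weight of one patient.* 1/46 = 2.2 percentage points. This is the weight of a single reclassified patient in an arm's rate, not an estimate of bias.

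*Attribution (assumptions; the documents give no event or attribution rates).* If the true event rate r is the same in two arms and the share of events called therapy-related differs by g, the spurious difference in recorded rates is r × g:

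| True rate r | g = 5 points | g = 10 points | g = 20 points |
|---|---|---|---|
| 20% | 1 point | 2 points | 4 points |
| 40% | 2 points | 4 points | 8 points |
| 60% | 3 points | 6 points | 12 points |

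*False differences (assumptions).* Take two arms of 46 with the same true rate, and let reporting add x points in one arm. By the normal approximation for two proportions, at two-sided 0.05, the chance of a significant difference in that direction is:

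| True rate | x = 0 | x = 5 | x = 10 | x = 15 | x = 20 |
|---|---|---|---|---|---|
| 30% | 2.5% | 7% | 17% | 32% | 50% |
| 50% | 2.5% | 7% | 16% | 30% | 50% |

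For scale, with recorded rates near 32% the standard error of a difference between two arms is √(2 × 0.32 × 0.68 / 46) = 9.7 points. Every entry in the attribution table except the 12-point one is smaller than that.

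**The case against.** The best defence is that D.1 discloses the limit itself: the sentence after the label confines blinding to the microbiota and immunology evaluation. That stands. Nothing is concealed; the fault is an over-broad label and a missing specification. It does not rescue the abstract, which ties the label to efficacy and safety with no qualifier.

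Four stronger readings are tempting, and the documents do not support them.

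- *That patients and staff are known to be unmasked, and that staff who know the regimen decide which events are recorded.* The text is silent on these roles and on who attributes events. It supports only the statement that no one else is described as masked.
- *That the whole safety comparison is unprotected.* Section B defines the safety profile as clinical, immunological and microbiota impact, and the laboratory analysis of the last two is masked. The gap is in the clinical part.
- *That the eradication rates will be biased.* The breath test has a numeric cut-off, and the use of histology is unquantified. The exposure is confined to reader-dependent results.
- *That a particular distortion, such as 8 points, is to be expected.* All arms are active quadruple regimens, and the documents give no reason to expect an attribution gap of any given size.

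It can also be said that the therapy-related wording is loose. Phase 2 applies it at baseline too, when nothing can yet be treatment-related. In addition, D.4 refers to a Tasks section that is not in the text available, and the reference list includes a side-effect scoring proposal that this text does not cite. Detail on adverse events may therefore exist elsewhere. This weakens any firm claim about how events are captured, but D.4 cites the Tasks section for statistical analysis, not for masking, and the Phase 2 wording as it stands still restricts what is recorded.

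Finally, recording all events is arguably an endpoint matter rather than a masking one. It belongs here because it takes attribution out of the main comparison, and attribution is where lack of masking would do most harm.

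**Conclusion.** The point holds in limited form, and the sponsor should act on it. The label is supported for the microbiota and immunology analyses. It is not supported for eradication, adherence or clinical adverse events. Exposure is greatest for adverse events, present for histology where it is used, and small for the breath test.

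The amount of bias cannot be estimated from the documents. The tables above rest on assumed event rates, attribution gaps and reporting excesses, and show only the range over which the problem would be negligible or serious. The conclusion about the label needs none of these assumptions. It rests on the text available, and would change if masking of further roles is in place and is stated.

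**What to change.** 1. In the abstract and D.1, limit the word blind to the microbiota and immunology laboratory analyses, and describe efficacy and clinical safety as open-label. If masking of other roles is actually in place, state it role by role instead: patients, treating staff, breath-test operators, pathologists, and assessors of adherence and adverse events.
2. In D.3, Phase 2, specify that the 1- and 12-month biopsies and breath samples go for reading under a code that does not show the arm.
3. In D.3, Phase 2, record all adverse events regardless of attribution. Compare arms on the all-event rate, and report attributed events second.

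The cost is a less favourable design label, coding of samples at the participating centres, and a slightly longer adverse event form. The documents do not say who reads the samples, so the effort of coding should be confirmed locally. Sample size, regimens and visits are unchanged.

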#### **D.4 Statistical Analysis**

Using the Statistical Package for the Social Sciences (SPSS) version 22.0 (IL, USA). The level of statistical significance will be for a p-value  $< 0.05$ . The normality of data distribution will be evaluated by Kolmogorov-Smirnov or Shapiro-Wilk tests. Continuous variables will be expressed as mean and standard deviation or median and interquartile range and categorical variables as frequency and percentage. The comparison of continuous variables will be made using the Kruskal-Wallis test or Anova test and categorical variables using the Chi-squared test. For the comparison of paired data the Wilcoxon test or Friedman test and the t-Student or Anova test will be used. Further statistical analysis of H. pylori eradication efficacy, gut microbiota and immunological changes is described in Tasks section. The genome sequences will be grouped in OTU according to their similarity. The alpha taxonomic richness and diversity of fecal samples will be expressed in observed species, Sobs index and Shannon index. The composition of fecal

microbiota will be expressed in rarefaction curves and the comparison of the differences in OTU richness with the t-Welch test. Immunological findings will be expressed by radar charts and representative FACS dot-plots. Additional statistical analyses will be defined throughout the study.

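### The blinding claimed for the microbiota and immune evaluation rests only on hiding the scheme; masking of visit and sampling day is not described, and the before-after objectives need it

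*Combined protocol and SAP*

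**What the plan says.** Section D.1 states: "Regarding the evaluation of gut microbiota and immunological changes, the study will be blinded". The only reason given is that "the researchers responsible for sequencing and immunological analysis will not know the therapeutic scheme applied". Visit, sampling day and sample coding are not mentioned.

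Phase 2 in section D.3 sets the collection times. Stool is taken "before (baseline), after stopping treatment (Day 10 or 14) and 1 month after treatment (Day 40 or 44"). For blood: "Blood samples will be collected and analyzed on 2 occasions: before (baseline) and 12 months after treatment". Phase 1 lists the five arms as "sequential, hybrid, concomitant with bismuth and two concomitants bismuth-free", without durations.

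Section B includes two objectives that concern change over time in all treated patients: "To evaluate the changes in gut microbiota after the *H. pylori* eradication therapy", and one that begins "To evaluate the immunological changes after the". Separate objectives compare these changes between regimens.

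Section D.4 says "Immunological findings will be expressed by radar charts and representative FACS dot-plots". It gives no rule for gating, for excluding samples or for choosing the plots, and it leaves additional analyses to be defined during the study.

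**The concern.** Masking protects a comparison only if it hides what is being compared. For the between-regimen objectives that is the scheme, which D.1 does hide. For the two before-after objectives it is the visit. All five arms are active, so a reader who does not know the scheme but can tell baseline from follow-up has everything needed to read the two differently. Section A already assumes that gut homeostasis changes after therapy, so the expected direction is known. No untreated arm exists in which a reading shift between visits would show up and could be subtracted.

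A second, smaller gap affects stool. The nominal post-treatment day follows treatment length (10 or 14, then 40 or 44). If length is set by scheme and the day appears on a label or in a file, it tells the reader which length group the sample belongs to.

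What is at stake is the credibility of the laboratory results where judgement enters: flow-cytometry gating, calls on failed samples, and sequence-processing choices. A reading shift between visits would be reported as an effect of therapy. A shift tied to length would be reported as a difference between regimens.

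**Working it through.** **The plan's own figure.** Section D.3 gives 46 per arm and 230 in total. With p = 0.864, margin 0.10 and z = 1.96, n = z² p(1−p)/d² = 45.14, which rounds up to 46, and 5 × 46 = 230. The figure reproduces. It is used below only as the number of patients, assuming equal arms and complete pairs.

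**What scheme masking covers**

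| Comparison | Must be hidden | Does D.1 hide it? |
|---|---|---|
| Before-after, stool | Visit | Not described |
| Before-after, blood | Visit | Not described |
| Between regimens, stool | Scheme, and any cue to it | Scheme yes; study day not described |
| Between regimens, blood | Scheme, and any cue to it | Scheme yes; the nominal schedule gives no cue |

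**What the stool day could disclose.** Assume two lengths fixed by scheme, with k arms of one length and 5−k of the other. The documents do not give k.

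- Chance of naming the arm without the day: 1/5 = 20%.
- Chance with the day: (k/5)(1/k) + ((5−k)/5)(1/(5−k)) = 1/5 + 1/5 = 40%, for any k from 1 to 4.
- Arm pairs separated by length: k(5−k) of 10. A 1/4 split separates 4, so 6 stay masked, and the single arm is fully identified. A 2/3 split separates 6, so 4 stay masked, and no arm is fully identified.

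For blood (baseline and 12 months) the nominal day is the same whatever the length, so the chance stays at 20%.

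**Sensitivity to a reading shift between visits.** Paired t-test, 230 pairs, two-sided 5% (D.4 gives 0.05 but not the sidedness). The SD of the change is √(2(1−ρ)), which is 1.000 at ρ = 0.5 and 0.775 at ρ = 0.7. Noncentrality = shift × √230 / SD of the change. Both the shifts and ρ are assumptions; no document supplies them.

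| Shift (SD) | Noncentrality, ρ = 0.5 | False-positive rate | Noncentrality, ρ = 0.7 | False-positive rate |
|---|---|---|---|---|
| 0.05 | 0.76 | 12% | 0.98 | 16% |
| 0.1 | 1.52 | 33% | 1.96 | 50% |
| 0.2 | 3.03 | 86% | 3.92 | 97% |

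**Sensitivity to a shift tied to length (stool only).** Five-arm ANOVA, 46 per arm, 4 and 225 degrees of freedom, with the shift in k arms in units of the SD of the analysed measure. Noncentrality = 46 × shift² × k(5−k)/5.

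| Shift (SD) | One arm: noncentrality, rate | Two arms: noncentrality, rate |
|---|---|---|
| 0.05 | 0.09, 5% | 0.14, 6% |
| 0.1 | 0.37, 7% | 0.55, 8% |
| 0.2 | 1.47, 13% | 2.21, 18% |

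The before-after comparisons are the more exposed: they pool all 230 patients, so even a small shift has a visible effect. The between-regimen test hardly moves until the shift reaches about 0.2 SD.

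**The case against.** **Silence is not disclosure.** No part of the text says the laboratories receive the study day, visit or date. Phase 2 is a collection schedule and says nothing about labels. Coded samples would be fully compatible with D.1. A reader might infer that the laboratories are in fact unmasked to visit and day; the documents do not support that. Section D.4 also refers to a Tasks section that is not in the available text and might cover sample handling. This stands, so the point is that the masking is not described. The anonymity promised in D.5 does not fill the gap: it protects patient identity in the database and does not address what the laboratory sees.

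**The day cue does not reach the immune evaluation.** It is tempting to apply the 10/14 and 40/44 argument to both kinds of outcome. Blood has no length-dependent day, so for immune outcomes only the visit question remains. This stands in full.

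**Length is not scheme.** One might also conclude that the day unmasks the between-regimen comparisons altogether. It does not: 4 to 6 of the 10 arm pairs would stay masked even if the day were visible, and full identification of one arm needs a 1/4 split that the documents do not establish.

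**Instrument readouts leave little to judgement.** Sequencing and Luminex output is largely machine-produced, and the dot-plots illustrate results without testing anything. This narrows the risk to gating, exclusions and pipeline choices but does not remove it, because D.4 fixes no rule for any of them.

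**Drift between visits would look the same.** Assay or batch drift over 12 months could produce the same pattern, and masking would not remove it. This is correct. It argues for mixed-order processing alongside masking and is no reason to leave the visit visible.

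**Conclusion.** The point holds as a gap in what the masking is stated to cover. D.1 rests its claim on hiding the scheme, and that gives no protection to the two pooled before-after objectives, for stool or blood. For the between-regimen stool comparisons the gap is partial and conditional: it needs the laboratory to see the day and length to be set by scheme, and even then it lifts the guess from 20% to 40% only.

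The false-positive rates (12% to 97% for the paired test, 5% to 18% for the ANOVA, over shifts of 0.05 to 0.2 SD) show how sensitive the tests are. They do not predict bias in this trial. They rest on assumed shifts and correlations, equal arms and complete data.

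The wider conclusion that the laboratory evaluation is unblinded is not supported. Sample size and eradication results are unaffected. This is a cheap improvement, to be made before samples are read, because readings taken with the visit visible cannot be masked afterwards without repeating the judgement steps.

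**What to change.** - Amend D.1 so that the laboratory researchers are masked to visit and study day as well as to scheme.
- Label stool and blood tubes, and sequencing and FCS files, with random codes that carry no visit, day or date. Hold the key outside the laboratories.
- Process stored samples in mixed order across visits and arms where feasible. The documents do not say whether blood is stored or run fresh. If it must be run on receipt, apply the masking to the FCS files at the gating step.
- Fix the gating strategy, the sample-exclusion rules and the OTU pipeline before the key is opened.

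**Cost:** protocol wording, coded labels, a sample key and a little more sample-tracking work. No extra patients, samples or visits are needed.

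**Limit:** masking does not remove assay drift between visits. Mixed-order processing helps only for samples that can be stored, and the lack of an untreated arm remains.
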